8.1.1. Overall Summary of Adverse Events

An overall summary of TEAEs will be provided which tabulates the number and percentage of subjects who experienced a TEAE, related TEAE, treatment-emergent SAE, treatment-emergent related SAE, treatment-emergent Grade 3 or higher AE, treatment-emergent infections of Grade 3 or higher severity, TEAE thromboembolic event, and TEAEs within 24 hours after the start of infusion; the number and percentage of subjects who discontinued treatment and/or the study due to an AE; and the number and percentage of subjects who died. In addition, the number of TEAEs, TESAEs, TEAE thromboembolic events and TEAEs within 24 hours after the start of infusion will be presented.

8.1.2. Treatment-emergent Adverse Events

The incidence of TEAEs will be summarized by SOC and preferred term.

8.1.2.1. Adverse Events in Descending Order of Incidence

Tables will be provided which display TEAE and TESAE preferred terms in descending order of incidence. Only preferred terms will be included in these tables (i.e., the display will not include SOCs).

A similar table will be provided for Grade 3 or higher TEAEs. AEs for which the assessment of severity is missing will be included in this table.

8.1.2.2. Severity of Adverse Events

AEs are classified by the Investigator for CTCAE grades v4.03. A summary of TEAEs by system organ class, preferred term, and CTCAE grade will be presented. AEs with a missing severity will be excluded from this table and listed separately to supplement the summary table. A subject will be counted once for each SOC and preferred term based on the greatest severity within that SOC and preferred term, respectively.

8.1.2.3. Relationship of Adverse Events to Study Drug

AEs are classified by the Investigator for relationship to study drug (“Not related,” “Possible,” and “Probable”). For summary tables, an AE with relationship of “Possible” or “Probable” will be considered “Related.” A summary of TEAEs by SOC, preferred term, and relationship (“Related” or “Not related”) will be presented. AEs with a missing relationship will be counted as “Related” in the summary table. A subject will be counted once for each SOC and preferred term based on the highest relationship within that SOC and preferred term, respectively.

8.1.3. Serious Adverse Events

Any AE reported as resulting in death, immediate risk of death (life threatening), inpatient hospitalization or prolongation of existing hospitalization, persistent or significant disability/incapacity, or a congenital/anomaly/birth defect will be classified as an SAE by the Investigator. An SAE may also be any other medically important event that, in the opinion of the Investigator, may jeopardize the subject or may require intervention to prevent one of the other outcomes listed above.

All SAEs will be listed; treatment-emergent SAEs and treatment-emergent related SAEs will be summarized by system organ class and preferred term.

8.1.4. Adverse Events Leading to Treatment Discontinuation and/or Study Withdrawal

AEs leading to treatment discontinuation and/or study withdrawal will be listed. All AEs reported on the AE log for the item “Action Taken with Study Drug” with a response of “Study drug permanently discontinued” or for the item “Was the subject terminated from this study due to this AE?” with a response of “Yes” will be included.

8.1.5. Deaths on Study

A listing of deaths occurring on study will be provided.

8.1.6. Adverse Events of Interest

8.1.6.1. AEs within 24 Hours after the Start of Infusion

All AEs within 24 hours after the start of infusion are captured in the eCRF. Incidence of AEs within 24 hours after the start of infusion will be summarized by SOC and preferred term.

8.1.6.2. Infections and Infections of \geq Grade 3 Severity

Infections will be captured based on MedDRA SOC of “infections and infestations.” Incidence of infections of Grade 3 or higher will be summarized by preferred term. Listings of all infections, infections of Grade 3 or higher and serious infections will be provided.

8.2. Clinical Laboratory Evaluations

Unless specified otherwise, all analyses described below will be performed on the Part B Study Period, starting at Week 27. All laboratory data will be provided in data listings; abnormal values relative to laboratory normal ranges will be identified.

8.2.1. Hematology and Chemistry

All summaries will be structured such that the hematology and chemistry tests are presented in the order shown in the tables below. All hematology and chemistry lab summaries will be analyzed using the Safety Analysis Set.

Hematology measurements that will be collected and listed include white blood cell count (WBC), red blood cell count (RBC), differentials (basophils, eosinophils, lymphocytes, monocytes, neutrophils, reticulocytes), hemoglobin, hematocrit, and platelet count.

Chemistry measurements that will be collected and listed include electrolytes (sodium, potassium, chloride), glucose, total protein, total bilirubin, alanine aminotransferase (ALT), aspartate aminotransferase (AST), alkaline phosphatase (ALP), blood urea nitrogen (BUN), and serum creatinine.

8.2.1.1. Change from Baseline

Hematology and chemistry results at baseline and Part B post-baseline visits, along with change from baseline, will be summarized with descriptive statistics. These by-visit summaries will be presented through the end of Part B.

8.2.1.2. Shifts

Each subject’s laboratory values will be classified according to whether the test result is “low” (below the LLN), “normal” (within the normal range), “high” (above the ULN). Shift tables will be constructed based on both the minimum and maximum post-baseline values for each subject. A separate table will be provided which summarizes the results of the shift tables in which the number and percentage of subjects with a shift to low (from normal, high, or unknown) and the number of subjects with a shift to high (from normal, low, or unknown) will be tabulated; percentages will be based on the number of subjects at risk. The number at risk for a shift to low (high) is the number of subjects whose baseline value was not low (high), including unknown, who had at least one post-baseline value. Only directions of change indicating a clinical concern will be included in this table summarizing the shifts. The direction of concern is provided in [Table 2](#).

All data collected during Part B, including data collected from unscheduled visits, will be included in the above-mentioned analyses.

Table 2: Direction of Change Indicating Clinical Concern for Laboratory Tests

Laboratory Test	Direction	Laboratory Test	Direction
Chemistry		Hematology	
Liver		White blood cells	Low and High
ALT/SGPT	High	Lymphocytes	Low and High
AST/SGOT	High	Neutrophils	Low and High
Total bilirubin	High	Monocytes	Low and High
GGT	High	Eosinophils	Low and High
Renal		Basophils	Low and High
Blood urea nitrogen	High	Red blood cells	Low and High
Creatinine	High	Hemoglobin	Low and High
Electrolytes		Hematocrit	Low and High
Sodium	Low and High	Platelets	Low and High
Potassium	Low and High		
Chloride	Low and High		
Other			
Glucose	Low and High		
Total protein	Low and High		

8.2.1.3. Potentially Clinically Significant Laboratory Abnormalities

Abnormal laboratory values (excluding LDH, haptoglobin, and reticulocytes) will also be evaluated by determining the number and percentage of subjects with at least one potentially clinically significant laboratory abnormality over the course of Part B of the study that also represents a worsening from baseline. The potentially clinically significant levels are based on Grade 2 or higher thresholds from the CTCAE v 4.03 where possible, or are defined by Bioverativ’s safety group. Subjects who have a post baseline laboratory value that meets the criteria for being potentially clinically significant but do not have a baseline value will be included in the numerator for determining the percentage of subjects with an abnormality.

All data collected during Part B, including data collected from unscheduled visits, will be included in this analysis.

8.2.2. Systemic Lupus Erythematosus (SLE) Panel

SLE panel (below) will be summarized with descriptive statistics for the Safety Analysis Set. The number of subjects with all negative results prior to receiving BIVV009, the number of subjects with at least one positive prior to receiving BIVV009, the number of subjects who tested negative at all post-baseline assessments, and the number of subjects who tested positive at any post-baseline assessment will be summarized for the individual SLE parameters as well as the combined (overall) SLE panel results.

Systemic Lupus Erythematosus Panel

Antinuclear antibody (ANA), multiplex with dsDNA, Anti-La/SSB antibody (SS-B), Anti-ribonucleoprotein antibody (RNP), Anti-Smith antibody (Sm), Anti-Ro/SSA antibody (SS A), Anti-scleroderma antibody (Scl-70), Anti-Chromatin antibody, Anti-Jo-1 antibody, Anti-Centromere B antibody, Circulating immune complexes (CIC).

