2.2.4 Potential risks and benefits

As previously noted, clinical proof of concept for BIVV009 was achieved in a Phase 1b study, which demonstrated immediate cessation of hemolysis and rapid correction of anemia during short-term treatment of patients with CAgD.

The human safety risk from off-target effects of mAb therapeutics is generally considered to be low, and in this regard BIVV009 is no exception. The human safety risk from short-term inhibition of the complement system also appears to be low, based upon the experience with five approved products in this therapeutic class. Long-term, complement inhibition may increase the risk of infection with encapsulated bacteria, as reflected in the product label for eculizumab (Soliris), an inhibitor of the terminal portion of the complement system. However, to provide optimal protection against infections with encapsulated bacteria, the design of this study includes an appropriate program of prophylactic vaccinations.

The risks associated with long-term inhibition of the proximal portion of the CP are presently unknown. Theoretically, it could increase the risk of SLE or circulating immune complexes (CIC) disease due to the role of the C1 complex in immune complex clearance, as observed in patients with congenital deficiencies of C1 complex components (C1q, C1s, and C1r). However, pharmacologic inhibition of C1s differs from congenital deficiency of the C1 complex because: 1) congenital C1 complex component deficiency are commonly not single gene mutations but typically are associated with second mutations in other immune system genes; 2) pharmacologic inhibition of C1s enzymatic function in the C1 complex leaves intact the non-enzymatic function of C1q, which is important for the opsonization and phagocytic removal of apoptotic cells which protects against autoimmunity; and 3) the phenotype associated with life-long, often total absence of C1 complex structure and function is unlikely to be reproduced by pharmacologic antagonism of C1 enzymatic function in fully developed adults. Nevertheless, standard clinical biomarkers related to SLE (eg, antibodies to double-stranded DNA [dsDNA]) have been incorporated into the study design as safety surveillance measures.

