5.2 EXCLUSION CRITERIA

Patients who meet any of the following criteria will be excluded from the study:

1. Cold agglutinin syndrome secondary to infection, rheumatologic disease, or active hematologic malignancy.
2. Clinically relevant infection of any kind within the month preceding enrollment (eg, active hepatitis C, pneumonia).
3. Clinical diagnosis of SLE; or other autoimmune disorders with anti-nuclear antibodies at Screening. Anti-nuclear antibodies of long-standing duration without associated clinical symptoms will be adjudicated on a case-by-case basis during the Confirmatory Review of Patient Eligibility ([Section 6.1.1.3](#)).
4. Positive hepatitis panel (including hepatitis B surface antigen and/or hepatitis C virus antibody) prior to or at Screening.
5. Positive human immunodeficiency virus (HIV) antibody at Screening.

6. Treatment with rituximab monotherapy within 3 months or rituximab combination therapies (eg, with bendamustine, fludarabine, ibrutinib, or cytotoxic drugs) within 6 months prior to enrollment.
7. Concurrent treatment with corticosteroids other than a stable daily dose equivalent to ≤ 10 mg/day prednisone for previous 3 months.
8. Erythropoietin deficiency. Concurrent treatment with erythropoietin is permitted if the patient has been on a stable dose for the previous 3 months.
9. Concurrent usage of iron supplementation unless the patient has been on a stable dose for at least 4 weeks.
10. Clinically significant medical history or ongoing chronic illness that would jeopardize the safety of the patient or compromise the quality of the data derived from his/her participation in this study (as determined by the Investigator [or designee]) at Screening.
11. Concurrent treatment with other experimental drugs or participation in another clinical trial with any investigational drug within 30 days or 5 half-lives, whichever is greater, prior to treatment start.
12. Females who are pregnant, lactating, or, if having reproductive potential, are considered potentially unreliable with respect to contraceptive practice.
13. History of hypersensitivity to BIVV009 or any of its components.

For country specific requirement - home infusion in/exclusion criteria see [Section 10.10](#), Appendix J.

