8.2.2. SLE Panel and Serum Disease-related Biomarkers

SLE panel (below) and serum disease-related biomarkers (below) at baseline and post baseline visits, along with change from baseline, will be summarized with descriptive statistics for the Safety Analysis Set. Additional exploratory analyses may be performed to examine the relationship between biomarkers and efficacy or safety parameters.

Systemic Lupus Erythematosus Panel

Antinuclear antibody (ANA), multiplex with dsDNA, Anti-La/SSB antibody (SS-B), Anti-ribonucleoprotein antibody (RNP), Anti-Smith antibody (Sm), Anti-Ro/SSA antibody (SS A), Anti-scleroderma antibody (Scl-70), Anti-Chromatin antibody, Anti-Jo-1 antibody, Anti-Centromere B antibody, Circulating immune complexes (CIC).

Disease-Related Biomarkers

DAT (polyspecific, anti-IgG & anti-C3d), LDH isoforms, cold agglutinin (CAg) titre, IgG subsets (IgA, IgD, IgG, IgM), CAg thermal amplitude. Vaccine titers, if collected, will be presented in a listing only.

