2.2. Study Endpoints

2.2.1. Safety Endpoints

The following are the safety-related endpoints for Part B:

- Incidence of treatment-emergent adverse events (TEAEs) and serious adverse events (SAEs)
- Change from baseline in clinical laboratory evaluations
- Change from baseline in systemic lupus erythematosus (SLE) panel
- Change from baseline in vital signs
- Change from baseline in electrocardiogram (ECG) data
- Physical examination findings
- Incidence of infections of \geq Grade 3 severity (i.e., requiring intravenous [IV] antibiotics)

Details of the analysis of safety endpoints are described in [Section 8](#).

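### The Part B SLE-panel summary does not split post-baseline positives by baseline status, so for any antibody with baseline positives it only bounds the number of newly positive patients

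*SAP*

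**What the plan says.** Part B SAP 2.2.1 lists as a safety endpoint "Change from baseline in systemic lupus erythematosus (SLE) panel". The analysis is in Part B SAP 8.2.2. It gives two counts before treatment: patients with every result negative, and "the number of subjects with at least one positive prior to receiving BIVV009". It gives two after treatment: "the number of subjects who tested negative at all post-baseline assessments", and the any-positive count, where "the number of subjects who tested positive at any post-baseline assessment will be summarized for the individual SLE parameters" and for the combined panel. The text names no cross-tabulation, no newly positive count and no at-risk denominator. Neither SLE table title in Part B SAP section 11 mentions a shift or a new positive.

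Protocol 2.2.4 explains why the panel exists. On long-term inhibition of the proximal classical pathway it says "Theoretically, it could increase the risk of SLE or circulating immune complexes (CIC) disease", and it adds that lupus biomarkers "have been incorporated into the study design as safety surveillance measures". Protocol 5.3 places newly positive lupus autoantibody titres among the adverse events that can lead to withdrawal. Protocol 5.2, criterion 3, excludes clinical SLE but leaves a route for some ANA-positive patients: "Anti-nuclear antibodies of long-standing duration without associated clinical symptoms will be adjudicated on a case-by-case basis".

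**The concern.** Change from baseline is a within-patient quantity. The planned counts describe the group before and after treatment without linking the two for any patient. A patient with long-standing ANA who stays positive and a patient who becomes positive on drug each add one to the same post-baseline count. The safety question is how many patients, negative at the start, developed an autoantibody during long-term C1s inhibition. Long-term safety is the primary objective of Part B, and this is the theoretical risk that the panel is meant to watch.

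The combined row has a further weakness. A patient who is ANA-positive at baseline and later gains a different antibody is positive at both times, so the new antibody leaves that row unchanged.

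The two halves also rest on different numbers of tests. The protocol schedule normally has one SLE panel before drug, at screening. After drug it has panels at Week 26, every 6 months in Part B and at the end-of-study visit. An any-positive count can only grow as panels are added.

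**Working it through.** The plan states no figure on this point, so there is nothing to reproduce. The check is whether the four counts determine the number of newly positive patients.

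**Set-up.** For one antibody, let N be the patients with both a baseline and a post-baseline result, b the baseline positives, p the patients positive at any later panel, and S the patients negative at baseline and positive later. The four planned counts are N − b, b, N − p and p.

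**Bounds.** At most b of the p later positives were already positive, so S ≥ max(0, p − b). S cannot exceed the later positives or the baseline negatives, so S ≤ min(p, N − b).

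**Inputs.** N = 20 is the approximate enrolment in Protocol 7.10. Part B is a subset of Part A, so its N may be smaller. The values of b and p are assumed, because the documents give none.

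| N | b | p | Smallest S | Largest S |
|---|---|---|---|---|
| 20 | 5 | 5 | 0 | 5 |
| 20 | 4 | 6 | 2 | 6 |
| 20 | 8 | 8 | 0 | 8 |
| 20 | 6 | 3 | 0 | 3 |
| 20 | 2 | 3 | 1 | 3 |
| 20 | 0 | 3 | 3 | 3 |

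An assumed N of 18 gives the same bounds in every row.

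**When the counts are enough.** S is fixed only if b or p equals 0 or N. At N = 20 there are 21 × 21 = 441 possible (b, p) pairs. Those with both values strictly between 0 and 20 number 19 × 19 = 361, which leaves 441 − 361 = 80 pairs where S is determined.

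**How wide the gap can be.** If p ≥ b, the width is at most p − (p − b) = b. If p < b, the width is at most p, which is below b. The uncertainty therefore never exceeds the number of baseline positives.

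**What it means as a rate.** With N = 20 and b = p = 5, the planned rows read 15 negative and 5 positive both before and after drug. They fit 0/15 newly positive (0%, exact 95% CI 0 to 21.8%) and equally 5/15 (33.3%, 11.8 to 61.6%). A cross-tabulation separates the two.

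**Comparison within the same SAP.** Part B SAP 8.2.1.2 gives hematology and chemistry shift tables with percentages over patients at risk. Part B SAP 8.2.3 gives incidence and prevalence for antidrug antibodies. The SLE panel has neither.

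**The case against.** The strongest reply is that nothing is lost. Part B SAP 8.2 puts all laboratory data in listings with abnormal values identified, and with about 20 patients each course can be read directly. That stands: a reader might infer that conversions would be hidden from the report, and the documents do not support this. The listings do not, however, replace a planned summary of a named endpoint.

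A second reply is that the counts suffice when nobody is positive at baseline for an antibody. That also stands. Clinical SLE is excluded, so this may be the case for several of the specific antibodies. It is not assured for ANA, or for the combined row.

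Third, the table shells are not in the documents and might already nest the later results under baseline status. That is possible, so the point concerns what the SAP text specifies.

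Two further inferences should be resisted. One is a numerical claim that repeat testing alone would create a signal. The documents give no rate of transient positivity, repeated results in one patient are unlikely to be independent, and the number of panels varies with time in Part B (Protocol 4.4 gives 2 to 3 years of dosing; the Part B SAP still describes a study ending 1 year after the last patient leaves Part A). Screening tests may also be repeated once (Protocol 6.1.1.1). The direction is clear, but its size cannot be stated. The other is that Part A shares the defect. Part A SAP 8.2.2 plans baseline and post-baseline results "along with change from baseline, will be summarized with descriptive statistics for the Safety Analysis Set", which is a different summary.

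**Conclusion.** The point holds as a gap in the planned Part B summary, and data collection is not affected. As written, Part B SAP 8.2.2 leaves the number of newly positive patients known only to within max(0, p − b) and min(p, N − b), for any antibody with at least one baseline positive and for the combined row. The gap is at most the number of baseline positives and is zero where there are none. The 0-to-5 example rests on assumed counts and shows the mechanism; it does not predict the trial's result. To say that the summary can never show seroconversion would go too far, since it is exact for antibodies with no baseline positives. The change is still worth making, because the endpoint is change from baseline, the risk is one the protocol itself names, and the SAP already uses paired or incidence summaries for other laboratory data.

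**What to change.** In Part B SAP 8.2.2, replace the four separate counts as follows.

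- For each antibody, cross-tabulate baseline status (negative or positive before BIVV009) by status at any post-baseline panel. Report newly positive patients over baseline-negative patients with at least one post-baseline result, as n/N.
- In the combined row, count patients with any newly positive antibody. Cross-tabulating overall panel status would still miss a new antibody in a patient already positive for another.
- Show new positives by visit as well as overall, because the overall count still accumulates with repeated panels. Flag whether each new positive was also positive on the next panel, and note that a first positive at the last panel cannot be confirmed.

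If the table shells already contain the cross-tabulation, a sentence in 8.2.2 saying so settles the first item. Using the same layout in Part A is optional. The cost is a revised table and one derived flag for positivity on the next panel. All the data are already collected.

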8.2.3. Anti-drug Antibody (ADA)

Subjects will be evaluated for anti-drug antibodies at Baseline and at the ET/EOS/Safety Follow-up visit in Part B. Subjects with negative or positive anti-drug antibodies at baseline and post baseline, as well as the incidence and prevalence will be summarized for the Combined Study Period. A listing will be provided for subjects with negative or positive anti-drug antibodies along with the associated titer if available. If applicable, TEAEs for those subjects will be included in the same listing.

